12.1 Amendment History

Current Version

Amendment 2: 18 NOV 2020

Previous Versions

Amendment 1: 08 JAN 2020

Original Protocol: 12 JUL 2019

12.2 Global Amendment 1

Amendment 1 is a global amendment forming integrated protocol Amendment 1, dated 08 JAN 2020.

Overall rationale for the amendment

The primary purpose of this amendment is to:

- 1) To further evaluate safety and efficacy of the regorafenib and nivolumab combination, sample size of the study will be increased from 53 to approximately 100 treated patients. The primary completion is defined by the event when the last enrolled participant was assessed for response rate as defined by RECIST v1.1 during at least 5 post-baseline scans i.e., has been followed for approximately 10 months from the first dose. With increased sample size of 100 patients, when the true underlying ORR is 17% or higher, there is >95% likelihood that the lower bound of the 95% CI will be above 5%. For this ORR analysis, the primary analysis will be based on blinded independent central review. In addition to ORR, duration of response will also be analyzed and reported descriptively.
- 2) To clarify inclusion criteria 5 regarding prior lines of treatment.
- 3) To modify exclusion criteria 5 to allow inclusion of patients with deep vein thrombosis and pulmonary emboli who have been adequately treated with anticoagulation.
- 4) To remove exclusion of participants with BRAF V600E mutation
- 5) To provide guidance regarding interrupting regorafenib treatment during on treatment biopsy.
- 6) To modify criteria for nivolumab discontinuation due to delay in dosing. Delay in nivolumab dosing that requires discontinuation has been changed to 10 weeks instead of 6 weeks to be consistent with other nivolumab studies using 480 mg dose Q4W.
- 7) To align wording for tolerance and escalation of regorafenib starting dose. Tolerance defined as: Absence of any grade rash/HFSR or other Grade 2 or higher clinically significant toxicity.

Changes to the protocol text

Changes to the protocol text are provided in a separate track-changes version.

High-level description of the changes and the affected sections are listed in the table below.

Table 12–1: Summary of Changes to the Protocol

Protocol Section	Amendment 1 Revisions
Throughout	Use RECIST v1.1 and iRECIST
1.1 Synopsis 3. Objectives and Endpoints	Modified footnote of Tables 1.1 and 3-1 Objectives and Endpoints: ORR and DOR will be based on blinded independent central review (BICR) and local investigator assessment per RECIST 1. The primary efficacy endpoint (ORR) will be based on the local investigator's assessment on blinded local investigator's assessment. Central independent central review (BICR) may be implemented as needed for ORR assessment by RECIST 1.1. DCR and PFS will be based on local investigator assessment.
1.1 Synopsis 4.1 Overall Design 5. Study Population 9.2 Sample Size Determination	Adjusted/modified wording to account for increased participant numbers (...approximately 143 instead of 80 ; treated 100 instead of 53 , approximately 50-60 instead of 30-35 for left sided tumor) and to reflect statistical implications for right- and left sided tumors, ORR and true underlying response rate: Approximately 143 participants will be screened to achieve 100 treated participants. Approximately 50-60 participants with left sided primary At least 100 participants who qualify for the study will be treated As of amendment 1, additional 47 patients will be treated to achieve approximately 100 treated patients. With increased sample size of 100 patients The location of the primary tumor is a factor and it is expected that 50-60 patients will have the primary tumor on the left side
1.2 Schema, Figure 1-1 4.1.1 Screening Phase, Figure 4-1, footnote a 4.1.2 Treatment Phase 4.3 Justification of Dose 6 Study Intervention	Alignment of wording for tolerance and escalation of regorafenib starting dose: Absence of any grade rash/HFSR or other Grade 2 or higher clinically significant toxicity
1.3 Schedule of Activities	Updated sampling timepoint for several screening assessments from 7 days prior to 28 days prior to first dose to allow more time for planning biopsy Added footnote 'c': If tested within 7 days prior to first dose no additional testing on D1 required except for pregnancy testing and abnormal liver function tests Added to footnote 'b': If disease progression and start of a new anti-cancer treatment happens before the 30/100 d safety visit, the safety visits should still be performed.
3 Objectives and Endpoints, Table 3-1	Removed reference to iRECIST v.1.1 as iRECIST is used.
4.1 Study Design 5.1 Inclusion Criteria #5	Modified details on prior lines of treatment: ...treated with no more than two (for extended RAS mutant) and or three (for extended RAS wild type) lines of systemic chemotherapy
4.1.2 Treatment Phase	Deleted " as determined by investigator " and central review is needed : Primary endpoint of the study is ORR measured by RECIST v1.1 as determined by investigator. ... by a vendor for BICR. central review is needed.
4.1.4 Long-Term Follow-Up	Added detail on consent withdrawal: Participants will be followed for overall survival or consent withdrawal or death or lost to FU
4.4 End of Study Definition	Modified definition of primary completion/clarification of appropriate terminology: The primary completion is defined by the event when the last all enrolled participants have been was assessed for response rate (as defined by RECIST v1.1) during at least 3 5 post-baseline scans unless they have discontinued before due to progression or any other reason i.e. have been followed for approximately 6 10 months from 1st dose
5.1 Inclusion Criteria #5	Added details on progression: Participant must have progressed

Protocol Section	Amendment 1 Revisions
	
(radiologically or clinically) or been was intolerant to no more than two (for extended RAS mutant) and or three (for extended RAS wild type) lines of systemic chemotherapy ...
 
Added details on prior lines of treatment: Reintroduction of previously administered chemotherapy containing oxaliplatin, irinotecan or 5-fluorouracil/capecitabine, without newly added biologics like EGFR inhibitor for RAS wild type patients and locoregional treatments such as hepatic arterial infusion therapy, or Yttrium-90 radioembolization should not be counted as separate lines of treatment.
 
Added: Adjuvant/neoadjuvant ...considered as one line of chemotherapy ...

5.1 Inclusion Criteria #9
	
Modified wording on tumor tissue requirements: Exceptions for patients with less than required no recent baseline tumor tissue may be considered ...

5.2 Exclusion Criteria #1
	
Added dMMR to reflect the IHC testing methodology and deleted BRAF V600E mutation to be consistent with Phase III protocol: Participants with dMMR/MSI-H colorectal cancer or BRAF V600E mutation


5.2 Exclusion Criteria #5
	
Modified language to allow inclusion of patients with deep vein thrombosis and pulmonary emboli who have been adequately treated with anticoagulation: Arterial thrombotic or embolic events such as cerebrovascular accident (including transient ischemic attacks) within 6 months before the start of study medication. Active pulmonary emboli or deep vein thrombosis that are significant or not adequately controlled on anticoagulation regimen

CCI [REDACTED]
	
CCI [REDACTED]

6.6.1.1 Nivolumab Treatment – Permanent Discontinuation 7.1 Discontinuation of Study Intervention
	
To modify criteria for Nivolumab discontinuation due to delay in dosing. Delay in nivolumab dosing that requires discontinuation has been changed from 6 weeks to 10 weeks.

7.1 Discontinuation of Study Intervention
	
Harmonized wording throughout section 7.1: Start of subsequent systemic anti-cancer treatment a new anti-cancer therapy.

8.1 Efficacy Assessment
	
Deleted: “as determined by Radiologist/Investigator”
 
Specified wording on tumor assessment: Primary endpoint for efficacy assessment is ORR based on BICR measured by per RECIST 1.1. as determined by Radiologist/Investigator. Radiological tumor assessments will be done locally by the investigator, and in addition centrally by a blinded independent central imaging review. Scans will be prospectively collected and stored at vendor in case for independent central review is needed BICR. Treatment response for primary efficacy endpoint (ORR) will be based on BICR. ORR and DOR will be assessed by BICR and local

Protocol Section	Amendment 1 Revisions
	
investigator per RECIST 1.1. DCR and PFS will be based on local investigator assessment. ... scans ... must be collected ... for in case blinded independent central review is needed. For patients with objective response (CR and PR), scans will be collected till start of subsequent systemic anti-cancer treatment.
 
Moved up subsection “Assessment of disease” for better understanding and added “CR and PR must be confirmed with repeated imaging performed at least 4 weeks after initial documentation of response.” to description of RECIST v1.1


9.2. Sample Size Determination
	
Rewrote and adjusted section to account for changed patient numbers: As of amendment 1, additional 47 patients will be treated to achieve approximately 100 treated response evaluable patients. With increased sample size of 100 patients, when the true underlying ORR is 17% or higher, there is >95% likelihood that the lower bound of the 95% CI will be above 5%. The sample size of 100 patients for a one-sided exact binomial test at a type-I error of at most 2.5% would result in a power of 96.4%, with at least 11 responders needed to achieve significance.
 
The sample size in this study was determined by the need to have a sufficient number of patients with the primary tumor located on each side (right and left). The location of the primary tumor is a factor and it is expected that 50-60 patients will have the primary tumor on the left side. This sample size of 53 patients for a one-sided exact binomial test at a type-I error of at most 5% would result in a power of 90.6%. Approximately 30-35 participants with left sided primary tumor will be treated. In order to allow appropriate balance of participants with right and left sided primary tumors, enrollment may be restricted to either left or right sided tumors during the study.
 
With 45 48 patients with right-sided tumors, the probability of observing 5 2 or more responders (ORR 11%) is approximately 90% 83% when the true underlying response rate is 17%, and the probability of observing 3 4 or fewer responders (ORR 6.6%) is approximately 81% 77% when the true ORR is 5%.
 
With 55 35 patients with left-sided tumors, the probability of observing 6 4 or more responders (ORR 11%) is approximately 92% 87% when the true underlying response rate is 17%, and the probability of observing 3 2 or fewer responders (ORR 6%) is approximately 70% 75% when the true ORR is 5%.
 
The critical number of responders to be achieved or surpassed to reject the null hypothesis of a 5% response rate for overall population is 6 patients.
 
For this calculation SAS PROC POWER was used.

9.4 Statistical Analysis
	
Correction; SAP will be finalized before database lock FPFV rather than at database lock as stated in the original version

9.4.1 General Considerations
	
Corrected error levels: All analyses will be conducted at one-sided type-I error level of 2.5% 5% or two-sided type-I error level of 5% 40% respectively


9.4.2 Primary Endpoints 9.4.3 Secondary Endpoints
	
Corrected confidence intervals to 95% from 50%. Added to 9.5.3: For patients that started subsequent therapy, PFS will be censored at the start of subsequent therapy.

9.5 Interim Analysis
	
Modified ...after approximately 50% of the 30-40 participants Correction; main data analysis may be conducted by study statistician and does not require an external statistician. Analyses do not require to be pre-specified in SAP. Deleted: ...due to the exploratory nature of this study... In order to avoid bias during the main analysis, the data look will be conducted by a statistician not involved in the study and the analyses to

Protocol Section	Amendment 1 Revisions
	be conducted will be pre specified in an interim SAP.
10.1.3 Informed Consent Process	Deleted non-required details: Only if the participant voluntarily agrees to sign the pharmacogenetics (PGx) research project informed consent form and has done so, optional study procedures can be performed (e.g., sample collection for optional biomarker testing).
10.2 Appendix 2: Clinical Laboratory Tests	Total Calcium assessment of chemistry panel changed to Calcium (total calcium), calcium ionized or adjusted calcium . Total bilirubin and indirect bilirubin changed to: total and direct bilirubin . Deleted assessments not required; RBC Indices, MCV, MCH, %Reticulocytes

In addition to the substantive changes summarized in above table, several changes were made to update administrative details, correct typographical errors, and add clarity; such changes are not itemized in the table.

Document Type:	Statistical Analysis Plan
Official Title:	An Open-label, Single-arm, Phase II Study of Regorafenib and Nivolumab in Patients with Mismatch Repair-Proficient (pMMR)/Microsatellite Stable (MSS) Colorectal Cancer (CRC)
NCT Number:	NCT04126733
Document Date:	11 NOV 2020

Table of Contents

Title page..... 1

Abbreviations..... 3

1. Introduction 4

2. Study Objectives..... 4

3. Study Design 4

4. General Statistical Considerations 4

4.1 General Principles..... 4

4.2 Handling of Dropouts 4

4.3 Handling of Missing Data..... 5

4.4 Interim Analyses and Data Monitoring 5

4.5 Analysis of long-term follow-up..... 5

4.6 Data Rules..... 6

4.7 Validity Review 6

4.8 Subgroup analyses 6

5. Analysis Sets 7

5.1 Assignment of analysis sets 7

6. Statistical Methodology 7

6.1 Population characteristics 8

6.2 Efficacy..... 8

6.2.1 Sample size..... 8

6.2.2 Primary Endpoint: Overall response rate (ORR) based on RECIST v1.1 9

6.2.3 Secondary endpoints..... 10

CCI [REDACTED]

6.5 Safety 11

6.5.1 Extent of exposure..... 12

6.5.2 Adverse events..... 12

6.5.3 Deaths and Serious Adverse events..... 14

6.5.4 Pregnancies..... 14

6.5.5 Clinical laboratory data 14

6.5.6 12-Lead ECG, QTc..... 16

6.5.7 ECOG status 17

6.5.8 Other safety measures..... 17

7. Document history and changes in the planned statistical analysis..... 17

CI [REDACTED]

Abbreviations

AE	Adverse event
Anti-PD-1	Anti-programmed cell death protein-1
BICR	Blinded independent central review
BMI	Body mass index
CI	Confidence interval
CRF	Case report form
CRC	Colorectal cancer
CSR	Clinical study report
CTCAE	Common terminology criteria adverse event
ECG	Electrocardiogram
FAS	Full analysis set
IMAE	Immune modulating adverse event
MedDRA	Medical dictionary for regulatory activities
MSS	Microsatellite stable CRC
N/A	Not applicable
NCI	National cancer institute
PD	Pharmacodynamics
pMMR	mismatch repair-proficient CRC
PK	Pharmacokinetics
QT	Q wave to T wave interval
QTc	Corrected QT
RECIST	Response evaluation criteria in solid tumors
SAE	Serious adverse event
SAP	Statistical analysis plan
TEAE	Treatment emergent AE
VEGF	Vascular endothelial growth factor
WHO	World health organization

CCI

2. Study Objectives

The purpose of this study is to determine the safety and efficacy of the combination of regorafenib and nivolumab in patients with advanced or metastatic pMMR/MSS colorectal cancer.

3. Study Design

This is an open-label single-arm study.

4. General Statistical Considerations

4.1 General Principles

The statistical evaluation will be performed by using the software package SAS release 9.2 or higher (SAS Institute Inc., Cary, NC, USA). All variables will be analyzed by descriptive statistical methods. The number of data available and missing data, mean, standard deviation, minimum, quartiles, median, and maximum will be calculated for metric data. Frequency tables will be generated for categorical data.

All data from the data base will also be given in subject data listings. Those will not be described in further detail as they will just represent the database.

4.2 Handling of Dropouts

All patients who discontinue the study after enrollment for any reason except death before the protocol defined end are considered drop-outs. Data of drop-outs will be used up to the point of study discontinuation, however no imputation for missing values will be done, except for dates (see below).

4.3 Handling of Missing Data

All missing or partial data will be presented in the subject data listing as they are recorded on the Case Report Form (CRF).

The number of subjects who prematurely discontinue the study and study treatment for any reason, as well as the reasons for premature discontinuation of study and study treatment, will be reported.

Missing or unevaluable tumor assessments, including scheduled assessments that were not done and incomplete assessments that did not result in an unambiguous tumor response evaluation according to RECIST 1.1, will not be used in the calculation of derived efficacy variables related to tumor assessments unless a new lesion occurred or the lesions that were evaluated already showed progressive disease. No imputation will be performed for missing lesion assessments and tumor response evaluation.

If a date is incomplete, (e.g. only year and month of date of tumor assessment or date of death is available), then day 15 of the month will be used for the calculation of, for example, overall survival and progression free survival. For imputation of AE dates, if the range of possible dates (e.g. a month, if day is missing) and during this time period “treatment emergent” and “non treatment emergent” is possible, the date will be imputed such that the AE will be “treatment emergent” (e.g. the day of treatment start if day is missing).

If the actual scan date of the radiological progression is missing and radiological or clinical progression has been documented based on criteria specified in the protocol, the scheduled scan date will be used to calculate the time to progression.

Safety variables, medical history and concomitant medications:

Treatment emergent AEs, treatment phases, period and relative days will be derived according to data management programming, the operations manual and standard guidelines.

4.4 Interim Analyses and Data Monitoring

No formal interim analysis is planned in this study.

However it is planned to look at the data after 30-40 participants have had at least the first response evaluation, in order to get better information for the planning of the intended Phase III study. This data look will be focused on the response data only and the analyses will be described in a separate data look SAP.

No formal conclusions for this study will be drawn from this look at the data and due to the exploratory nature of this study, no formal adjustment of the type-I error will be performed.

4.5 Analysis of long-term follow-up

During the long term follow-up data on survival and subsequent anti-cancer therapies are collected by either telephone contact or onsite visit. After the last patient finished the long-term follow-up, a final analysis of the long-term follow-up will be conducted. This will be conducted on the follow-up set of patients and will include population characteristics, overall survival analysis and anti-cancer medication. Details of the FU analysis will be specified in a separate document, either as addendum to this SAP or in a separate SAP.

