4.1.3 Active Follow-Up

A mandatory clinical visit to monitor safety will take place 30 d (window of +7 d) after the last administration of regorafenib/nivolumab and 100 d (window of +7 d) after the last dose of nivolumab. Longer safety FU for nivolumab is required due to the long half-life of the antibody.

Participants who discontinue study intervention due to radiologically progressive disease will terminate the active FU period after the clinical safety visits.

Participants, who have not progressed clinically or radiologically or have discontinued study intervention for reasons other than death, withdrawal of consent or lost to FU, will continue with radiological tumor assessments. During the active follow-up period, CT (computed tomography) /MRI (magnetic resonance imaging) evaluations will be performed at the same intervals as during study treatment (every 8 weeks for the first year, and thereafter, every 12 weeks). In addition, study intervention-related toxicity/AE and information about survival status and subsequent anti-cancer therapy will be followed up until completion of the active FU.

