4.1.4 Long-Term Follow-Up

[figure not shown]
All surviving participants will enter the long-term FU period after discontinuing from the active FU period except for participants who explicitly withdraw consent or are lost to FU. Participants will be followed for overall survival and subsequent anti-cancer therapy at 3-month intervals (\pm 14 d) until end of study, 2 years after the last participant started study intervention (telephone contact is sufficient) or consent withdrawal or death or lost to FU. Participants may be contacted at additional times throughout the course of the study in order to collect survival data to ensure that long-term FU data is current.

CCI

CCI

patients with mCRC. Primary endpoint for the study is ORR by RECIST, which is an

CCI

CCI

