9.3 Populations for Analyses

The following populations are defined:

Table 9–1: Populations for Analyses

Population	Description
Enrolled	All participants who sign the ICF
FAS	All participants who have received at least 1 dose of study intervention will be included in the efficacy and safety evaluation.
r-PKS	All patients who have received at least 1 dose of regorafenib and with at least 1 valid regorafenib concentration after dosing and no protocol deviations affecting the validity of the regorafenib PK will be included in the regorafenib PK analysis set.
n-PKS	All patients who have received at least 1 dose of nivolumab and with at least 1 valid nivolumab concentration after dosing and no protocol deviations affecting the validity of the nivolumab PK will be included in the nivolumab PK analysis set.
IMS	All patients who have received at least one dose of nivolumab and have at least one ADA sample taken (during the treatment or follow-up observation period) that is appropriate for ADA testing (with reportable result) will be included in the analysis set for the immunogenicity analysis of nivolumab, which is defined as the immunogenicity analysis set.

Abbreviations: ADA = anti-drug antibodies; FAS = full analyses set; ICF = informed consent form; PK = pharmacokinetics; r-PKS = regorafenib PK analysis set; n-PKS = nivolumab PK analysis set; IMS = immunogenicity analysis set

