5.1 Assignment of analysis sets

Final decisions regarding the assignment of subjects to analysis sets will be made during the validity review of study data and documented in the final list of important deviations, validity findings and assignment to analysis set(s) (see section 4.7).

Population	Description
Enrolled	All participants who sign the ICF
FAS	All participants who have received at least 1 dose of study intervention will be used for efficacy analysis.
SAF	All participants who have received at least 1 dose of study intervention will be used for safety analysis.
IMS	All patients who have received at least one dose of nivolumab and have at least one ADA sample taken (during the treatment or follow-up observation period) that is appropriate for ADA testing (with reportable result) will be included in the analysis of the immunogenicity of nivolumab, which is defined as the immunogenicity analysis set.
Follow-Up (FUP)	All patients who entered the long-term follow-up and have had at least one data collection during the long-term follow-up will be analyzed in the final analysis after study end.

Abbreviations: ADA = anti-drug antibodies; FAS = full analyses set; ICF = informed consent form; PK = pharmacokinetics; r-PKS = regorafenib PK analysis set; n-PKS = nivolumab PK analysis set; IMS = immunogenicity analysis set

No additional treatment assignments to compensate for potential unevaluable patients (e.g. lack of post baseline tumor scans) beyond the needed number of 70 treated patients is planned. Therefore SAF and FAS will be equal and only FAS will be referenced in the analyses.

6. Statistical Methodology

All variables will be analyzed at least descriptively, which includes summary statistics (N, mean, std. dev. minimum, median, maximum) for continuous variables and frequency tables (N, % per category) for categorical variables.

A confirmatory analyses will be conducted only for the primary endpoint at one-sided type-I error level of 2.5% or two-sided type-I error level of 5% respectively. No further confirmatory analysis is intended, and no further tests are conducted. Confidence intervals will be presented for selected variables.

Covid-19:

All COVID-19 related findings will be presented as a separate listing and in applicable tables (e.g. protocol deviations) as separate finding as well.

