6.2 Efficacy

Analyses will be based on the FAS population.

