6.2.3 Secondary endpoints

Overall survival (OS):

Overall survival is defined as the time (days) from the date of first treatment to the date of death.

OS for subjects who are still alive and in the study or who are lost to follow-up at the point of analysis will be censored at the last available date.

OS for subjects who have no post baseline information will be censored at day 1.

Progression free survival (PFS):

PFS is defined as the time (days) from the date of first treatment to the date of radiological or clinical disease progression or death due to any cause, if death occurs before progression is documented.

PFS for subjects without radiological or clinical tumor progression or death at the time of analysis will be censored at their last date of tumor evaluation.

PFS for subjects who have no tumor assessment post baseline and are still alive will be censored at day 1. Patients that report a PD after missed tumor assessment(s) will be censored at the last scan date the patient was known to be progression free.

Disease control rate (DCR):

Disease control rate is defined as the proportion of patients whose best response was complete response (CR), partial response (PR) or stable disease (SD). DCR will be evaluated at 8, 16, 24, 32 and 40 weeks

Scans collected after first progression disease (PD) will not be considered.

Duration of response (DOR):

Duration of response (for PR and CR) is defined as the time (days) from the first documented objective response of PR or CR, whichever is noted earlier, to disease progression or death (if death occurs before progression is documented). Duration of response will be defined for responders only, i.e. subjects with CR or PR.

Time to response (TTR):

Time to response is defined as the time (days) from first treatment until CR or PR and will be derived for responders only.

Duration of stable disease (DoSD):

[figure not shown]

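### The end-of-study overall survival analysis is assigned to patients who survived into long-term follow-up, so earlier deaths are left out and OS reads too high for treated patients

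*SAP*

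**What the plan says.** SAP 4.5 plans a final analysis once the last patient has finished long-term follow-up: "This will be conducted on the follow-up set of patients and will include population characteristics, overall survival analysis and anti-cancer medication". SAP 5.1 defines the follow-up set as "All patients who entered the long-term follow-up and have had at least one data collection during the long-term follow-up" and assigns it to the final analysis after study end. SAP 4.5 adds: "Details of the FU analysis will be specified in a separate document, either as addendum to this SAP or in a separate SAP".

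Entry to that period is set by the protocol. Section 4.1.4 says "All surviving participants will enter the long-term FU period after discontinuing from the active FU period", apart from those who withdraw consent or are lost. For progressors, section 4.1.3 says "Participants who discontinue study intervention due to radiologically progressive disease will terminate the active FU period after the clinical safety visits"; the later of those visits is 100 days after the last nivolumab dose. Appendix 6 can be read as letting patients who leave treatment with radiological progression go straight to survival follow-up.

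The endpoint and the general efficacy population are defined elsewhere. SAP 6.2.3 says "Overall survival is defined as the time (days) from the date of first treatment to the date of death". SAP 6.2 says "Analyses will be based on the FAS population". In Protocol 9.3 the FAS reads "All participants who have received at least 1 dose of study intervention will be included in the efficacy and safety evaluation", and that table contains no follow-up set.

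**The concern.** A patient must be alive to enter long-term follow-up, so anyone who dies on treatment or in active follow-up is not in the set. Everyone in the set carries survival time from first dose to entry during which they could not have died. Counting OS from first dose in such a set, without delayed entry, is immortal-time bias. The plan expects early deaths: SAP 6.5.3 tabulates deaths within 30 and 100 days of last dose.

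OS is a listed secondary endpoint, and Protocol 9.4.3 mentions rates at 6, 12 and 18 months. Primary completion comes when the last patients have about 10 months of follow-up (Protocol 4.4), whereas study end requires at least 24 months for the last participant. The better-matured OS would therefore come from a set selected on survival. It would not estimate OS for treated patients and would not be comparable with the earlier FAS figure.

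**Working it through.** **The plan's own figures.** The documents contain no OS assumption, treatment duration or entry time, so there is no OS figure to reproduce. The 70 treated patients come from SAP 6.2.1 and the 30.44 days per month from SAP 4.6. Everything else below is an assumption.

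**Fixed entry time.** Take exponential OS with true (FAS) median M months and entry to long-term follow-up at L months. Then:

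- share kept = 2^(−L/M)
- median in the follow-up set = M + L
- OS at t in the follow-up set = 2^(−(t−L)/M), against 2^(−t/M) in the FAS

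Three entry times are shown: 1 month; 56 days (56/30.44 = 1.84 months, the first 8-week scan, under the Appendix 6 reading); and 100 days (100/30.44 = 3.29 months, the earliest completion of the safety visits under Protocol 4.1.3). With M = 12:

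| Set | Kept | Dropped of 70 | Median (months) | 12-month OS | 18-month OS |
|---|---|---|---|---|---|
| FAS | 100% | 0 | 12.0 | 50.0% | 35.4% |
| Follow-up set, L = 1 | 94.4% | 3.9 | 13.0 | 53.0% | 37.5% |
| Follow-up set, L = 1.84 | 89.9% | 7.1 | 13.8 | 55.6% | 39.3% |
| Follow-up set, L = 3.29 | 82.7% | 12.1 | 15.3 | 60.4% | 42.7% |

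For M from 8 to 15 months, entry at 100 days drops 25% to 14% of patients (17.3 to 9.9 of 70) and adds 3.3 months to the median each time.

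**Variable entry.** Real entry follows the end of treatment, so it varies between patients. Three simulated models were used, each with a true median of 12 months:

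- *Treatment end independent of death* (exponential, median 2 or 4 months; entry 0, 1 or 3.29 months later; study end 24–34 months after first dose): about 62–86% kept, median about 14.6–20.0 months, 12-month OS 58–76%.
- *Treatment ends at progression, no deaths on treatment* (progression median 2 or 4 months, same delays): median 11.9–15.3 months, 12-month OS 50–65%.
- *Progression-based, with 10–20% of treatment-ending events being deaths*: median 12.9–19.4 months.

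**Offset.** The set also omits patients alive but still on treatment or in active follow-up at study end, who are likely long survivors. If they are a share q of the FAS, then for t up to 24 months:

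S(t) = (2^(−t/M) − q) / (2^(−L/M) − q), so the median solves 2^(−t/M) = (2^(−L/M) + q)/2.

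With M = 12:

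- L = 3.29: q = 3% gives (0.827 + 0.03)/2 = 0.429 and a median of 14.7 months; q = 5% gives 14.3.
- L = 1: q = 3% gives (0.944 + 0.03)/2 = 0.487 and a median of 12.5 months; q = 5% gives 12.1.
- The median shift vanishes when q = 1 − 2^(−L/M): 17.3% (about 12 of 70) for L = 3.29, or 5.6% (about 4 of 70) for L = 1.

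In a separate progression-based simulation (entry 100 days after the last 4-weekly nivolumab dose, or at progression if later), fewer than 2 of 70 patients had not entered by 24 months.

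**The case against.** The strongest reply is that the follow-up analysis is openly unfinished. SAP 4.5 leaves its details to a later document, which could specify delayed entry or add a FAS table. SAP 6.2 also puts efficacy, including OS, on the FAS without a time limit, so SAP 4.5 could be read as a supplement. This stands in part: a FAS-based OS will exist for the main report, and a later document can still put matters right. But the set is not among the deferred details, since SAP 4.5 and 5.1 both name it, and no text says OS is updated on the FAS at study end. The only OS time origin stated is first treatment.

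A second reply concerns size. The upper end of the first simulation depends on treatment end being independent of death. In the progression-based model without on-treatment deaths the shift is at most 3.3 months, and with immediate entry it disappears. That caveat stands, and 20.0 months and 76% should be read as the result of one model. The null result, however, needs both zero delay and no on-treatment deaths.

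Third, 10 months is the follow-up of the last patients; earlier ones have more. With a 12-month median, 1 − 2^(−10/12) = 44% would have died by month 10. How mature the FAS median and 12-month rate will be cannot be judged without the accrual pattern; the 18-month rate is the weaker one.

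Finally, a death reported at the first long-term contact may count as a data collection, so those deaths are not claimed as excluded.

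**Conclusion.** The concern holds. As written, the end-of-study OS is computed on a set selected on survival, with time counted from first dose, and this overstates OS for treated patients. With exponential OS and a 12-month true median, the median rises by 1.0 month for entry at 1 month and by 3.3 months for entry at 100 days, and 12-month OS rises by 3 and 10 percentage points. The size depends on assumed survival, entry time and on-treatment deaths, none of which the documents give. The net shift can be small if entry is very early or if enough long survivors are still outside the set at study end, but two selection effects cancelling by chance would still not give OS for the treated population. OS is descriptive, and neither the ORR test nor the OS at primary completion is affected. It should be fixed, but it does not threaten the primary result.

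**What to change.** In SAP 4.5 and 5.1, and in the planned addendum or separate SAP, state that the final OS analysis (Kaplan-Meier curve, median, and 6-, 12- and 18-month rates) is run on the FAS from first dose, with deaths and last-known-alive dates taken from all study periods. Keep the follow-up set for describing subsequent anti-cancer therapy. If OS is also shown on that set, label it as conditional on entry and use delayed entry.

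The cost is SAP wording only. The schedule of activities already collects survival status at end of treatment and in active and long-term follow-up, and Protocol section 7 requires deaths during treatment and the safety window to be reported, so no new data are needed. The reported end-of-study OS would probably be less favourable.
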